While these preliminary studies show promising results, important questions remain unanswered. These include: Can patients use self-guided Smart Glove therapy in their home or rehabilitation environment in addition to their routine rehabilitation therapy in the sub-acute

stroke period? Is the addition of Smart Glove therapy to routine rehabilitation therapy beneficial for recovery of arm and hand function? We will address these questions in the vREHAB study.

Primary Hypothesis

Our hypothesis is that self-directed use of the Smart Glove is feasible for subacute as well as chronic stroke patients, results in an increased dose of upper extremity rehabilitation, and leads to improved functional outcome and quality of life for stroke survivors.

Specific Aims

Aim 1: Demonstrate the feasibility of increasing the dose of rehabilitation in acute stroke patients with the Smart Glove. We hypothesize that patients randomized to the Smart Glove will have more upper extremity therapy than patients randomized to standard of care therapy.

Aim 2: Demonstrate the effect of Smart Glove use on functional recovery. We hypothesize that patients randomized to Smart Glove will have a greater improvement in arm/hand function as assessed on the Jebsen Taylor Hand Function (primary efficacy outcome) and Fugl-Meyer tests at the end of the intervention period, and that this improvement is sustained 12 weeks after completion of the intervention.

Aim 3: Demonstrate the effect of Smart Glove use on quality of life. We hypothesize that, compared to controls, patients randomized to Smart Glove will have a greater improvement in self-rated stroke related disability and quality of life (assessed with the Stroke Impact Scale) at the end of the intervention period, and that this improvement is sustained 12 weeks after completion of the intervention.

Relevance

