- Research coordinator will review the research consent form in detail with the participant and answer any questions about the study. After informed consent, the participant will be enrolled in the study, and baseline demographics will be collected.
- Smart Glove training for patient and caregiver
- Issuance of Smart Glove and tablet with preloaded software
- Modified Rankin Scale and NIHSS scoring
- Baseline testing of the affected extremity:
 - Jebsen-Taylor hand function test (JTHFT)
 - Upper Extremity Fugl-Meyer assessment (FM)
 - Manual muscle testing (MMT)
 - Shoulder Abduction/Finger Extension (SAFE) score of Predicting Recovery Potential (PREP) algorithm → 72h post-stroke (retrospective) and at enrollment

Day 7, 14, 21, 28 and 35:

- Phone call for patient compliance and troubleshooting

Day 42, follow-up visit #1 (mid-intervention):

- Discussion regarding patient compliance and troubleshooting
- Document amount of rehabilitation from PT/OT session log
- Testing of the affected extremity:
 - Fugl-Meyer assessment (FM)
 - Jebsen-Taylor hand function test (JTT)
- Download of patient use data from tablet (SmartGlove arm only)

Day 49, 56, 63, 70 and 77:

- Phone call for patient compliance and troubleshooting

Day 84 follow-up visit #2 after routine clinical follow-up appointment (end-intervention):

- Assess amount of rehabilitation from PT/OT session log
- Modified Rankin Scale

- Testing of the affected extremity and quality of life:
 - Jebsen-Taylor hand function test (JTHFT)
 - Fugl-Meyer assessment (FM)
 - Manual muscle testing (MMT)
- Stroke Impact Scale (SIS)
- Download of patient use data from tablet (SmartGlove arm only)
- User experience survey (SmartGlove arm only)

Day 91, 98, 105, 112, 119, 126, 133, 140, 147, 154, 161:

- Phone call for patient compliance and troubleshooting

Day 168 follow-up visit #3 (end-study):

- Assess amount of rehabilitation from PT/OT session log
- Modified Rankin Scale
- Testing of the affected extremity and quality of life:
 - Jebsen-Taylor hand function test (JTHFT)
 - Fugl-Meyer assessment (FM)
 - Manual muscle testing (MMT)
- Stroke Impact Scale (SIS)

Table 1. Schedule of Events							
Time-point	Week 0	Weeks 1 – 5	Week 6	Weeks 7 – 11	Week 12	Weeks 13 – 23	Week 24
Informed Consent	X						
Demographics	X						
Medical History	X						
Compliance Phone-Calls		X		X		X	
SAFE score (at 72h and at enrollment)	X						
Modified Rankin Scale (mRS)	X				X		X
NIHSS assessment	X						

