Jebsen Taylor Hand Test (JTHT)	X		X		X		X
Upper Extremity Fugl-Meyer (FM)	X		X		X		X
Manual Muscle Testing (MMT)	X				X		X
Stroke Impact Scale (SIS)					X		X
Assess amount of rehabilitation			X		X		X
User Survey (Smart Glove arm)					X		

Data analyses: All efficacy analyses are analyzed under the intention to treat principle. The primary efficacy outcome is the change in score on the Jebsen Taylor Hand Test between baseline and week 12. Secondary efficacy endpoints are changes in scores on the upper extremity Fugl-Meyer Scale, modified Rankin Score, total NIHSS score, Manual Muscle testing (of the biceps, triceps, wrist extensors, finger flexors, and finger abductors), Stroke Impact Scale, and total dose of rehabilitation received during the 12-week intervention period. Persistence of the treatment effect will be tested by comparing changes in scores on the Jebsen Taylor Hand Test and Fugl-Meyer upper extremity score at 24 weeks between treatment groups. Differences between treatment groups will be assessed using a generalized linear model (GLM) that accounts for repeated measures (assessments at baseline, 6 and 12 weeks for primary outcome, as well as 24 weeks for secondary outcome) and will be adjusted for imbalances in baseline variables. We will use a two-sided test with an alpha of 0.05 to declare significance. Based on prior studies we assume to see an 11.0-point improvement on the JTHF

test in patients who use the glove, a 3.0-point improvement in control subjects, and a standard deviation of the change score of 2.0.(1) Based on these assumptions we will have more than 90% power to show a significant effect of the use of the Smart Glove on our primary efficacy outcome.

Risks

Potential risks and inconveniences include that the participant will need to travel to Stanford for 3 follow-up visits over the course of the study. One may also experience technical difficulties in using the Smart Glove system. There is a low likelihood of one having a skin reaction to the material used to make the Smart Glove.

Benefits

While there is no definitive evidence that SmartGlove therapy will benefit patients, a potential benefit is that the participant may experience improvement in the function of their affected upper extremity as a result of study participation.

Withdrawal

Each subject and the investigator reserve the right at any time to terminate a subject's participation in the clinical investigation. Possible reasons for study withdrawal:

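### Two secondary endpoints are defined as changes that the visit schedule cannot supply: the SIS has no baseline and the NIHSS has no follow-up, so Aim 3 (SIS) cannot be tested as stated

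*Combined protocol and SAP*

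**What the plan says.** The Data analyses section defines the secondary outcomes as changes: "Secondary efficacy endpoints are changes in scores on the upper extremity Fugl-Meyer Scale, modified Rankin Score, total NIHSS score, Manual Muscle testing". The list ends with "Stroke Impact Scale, and total dose of rehabilitation received during the 12-week intervention period". Counting each item once gives six: Fugl-Meyer (FM), modified Rankin (mRS), NIHSS, manual muscle testing (MMT), SIS and rehabilitation dose. The same section compares the arms with a repeated-measures model whose assessments begin at baseline.

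Aim 3, under Specific Aims, predicts "greater improvement in self-rated stroke related disability and quality of life (assessed with the Stroke Impact Scale) at the end of the intervention period", and further that "this improvement is sustained 12 weeks after completion of the intervention". It names no instrument other than the SIS.

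On timing, the Day 0 list under Study Procedures includes "Modified Rankin Scale and NIHSS scoring" but no SIS. The Day 42, 84 and 168 lists contain no NIHSS. The SIS appears on Days 84 and 168. In Table 1 the row "NIHSS assessment" has one mark, under week 0, and the SIS row has two, under weeks 12 and 24.

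**The concern.** A change score needs a value before treatment and a value after it. The SIS has only the second and the NIHSS only the first, so neither endpoint exists as defined.

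The consequences differ:

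- **NIHSS.** Nothing is measured after randomization, so no efficacy comparison of any kind is possible.
- **SIS.** The only change the schedule allows runs from week 12 to week 24. That interval starts when the glove is returned, so it cannot show the effect of the intervention period.

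Quality of life is one of the trial's three stated purposes, and the SIS carries it alone. Someone will have to choose a substitute analysis: the week-12 score, the week-24 score, or the change between them. If the choice is made after results are seen by arm, it is post hoc.

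**Working it through.** **1. Endpoint list against schedule.** Time points are from Table 1, checked against the Day 0, 42, 84 and 168 lists.

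| Secondary endpoint | Wk 0 | Wk 6 | Wk 12 | Wk 24 | Change from baseline? |
|---|---|---|---|---|---|
| FM | X | X | X | X | yes |
| mRS | X | – | X | X | yes |
| MMT | X | – | X | X | yes |
| NIHSS | X | – | – | – | **no** |
| SIS | – | – | X | X | **no** |
| Rehabilitation dose | – | X | X | X | not needed (a total) |

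Table 1 and the visit lists agree for both scales, so a table damaged in conversion does not explain the gaps. Data Collection, Transfer, and Storage names the NIHSS and SIS among the data to be entered but adds no time point.

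**2. Count.** Two of the six named endpoints, or two of the five that are score changes, have the required pair of values in 0% of patients.

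**3. Persistence.** The 24-week persistence test in Data analyses names only the Jebsen Taylor test and the FM. The second half of Aim 3 therefore has no explicit SIS test either.

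**4. Stated power.** The plan gives no power for the SIS or NIHSS. Its one figure, more than 90%, is for the primary outcome (difference 11.0 − 3.0 = 8.0, SD 2.0, two-sided alpha 0.05). It reproduces: power exceeds 0.999 with 20 or 40 per arm. It has no bearing on this point.

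**5. What a baseline SIS would add.** The correlation ρ between baseline and week-12 SIS is not in the documents, so it is assumed. With n per arm, 80% power, two-sided alpha 0.05 and no dropout, the minimum detectable differences in SD units of the SIS score are:

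- follow-up score only: (1.960 + 0.842) × √(2/n)
- change score: the above × √(2(1 − ρ))
- follow-up score adjusted for baseline: the above follow-up value × √(1 − ρ²)

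For 80 patients (n = 40), follow-up only gives 2.802 × √(2/40) = 0.63. For 40 patients, the number given for Stanford alone (n = 20), it gives 2.802 × √(2/20) = 0.89.

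| ρ (assumed) | Change, N = 80 | Adjusted, N = 80 | Change, N = 40 | Adjusted, N = 40 |
|---|---|---|---|---|
| 0.3 | 0.74 | 0.60 | 1.05 | 0.85 |
| 0.5 | 0.63 | 0.54 | 0.89 | 0.77 |
| 0.7 | 0.49 | 0.45 | 0.69 | 0.63 |
| 0.8 | 0.40 | 0.38 | 0.56 | 0.53 |

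Using baseline as a covariate cuts the variance of the week-12 comparison by ρ² relative to unadjusted week-12 scores: 0.5² = 25% to 0.7² = 49%. A plain change score gains nothing at ρ = 0.5 and does worse at ρ = 0.3.

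**The case against.** The strongest reply is that little is lost. Under 1:1 randomization the expected difference between arms in week-12 SIS score equals the expected difference in change from baseline. A repeated-measures model can be fitted to the two follow-up values, and the week-24 value bears on whether any benefit lasts. The NIHSS belongs to no specific aim. The primary outcome is intact, and FM, mRS and MMT can all be computed. On this view the matter is a mismatch in secondary endpoints that rewording cures.

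Much of that is right, and it sets limits on the point. The Aim 3 problem comes from the SIS alone. A model of follow-up SIS scores is feasible; what cannot be fitted is a model that starts from a baseline assessment. The variance gain rests on an assumed correlation, and it would be smaller against an analysis already adjusted for baseline mRS and FM.

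The contradiction itself remains. A comparison of follow-up scores is not the endpoint written down. It cannot show improvement within an arm, and it cannot correct for a chance imbalance in baseline SIS; none of the minimization factors (age, time from onset, finger extension score, site) measures quality of life. For the NIHSS there is no fallback.

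**Conclusion.** The concern holds and must be fixed. Change in NIHSS and change in SIS cannot be computed for any patient under the plan as written. The NIHSS endpoint is empty. Aim 3 loses its stated analysis, although a valid randomized comparison of week-12 and week-24 SIS scores remains open.

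This conclusion rests on the text alone and needs no assumption. Only the precision figures do: with ρ assumed between 0.5 and 0.7, a baseline SIS used as a covariate would lower the detectable week-12 difference from 0.63 SD to between 0.54 and 0.45 SD for 80 patients, assuming no dropout.

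**What to change.** **SIS, no new data needed.** Restate Aim 3 and the endpoint as the difference between arms in SIS score at week 12, with week 24 as the persistence comparison, adjusted for the minimization factors and for baseline mRS and FM. Fix this before any outcome is examined by arm.

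**SIS, if patients remain to be enrolled.** The documents do not say how many do. Add the questionnaire at Day 0 as a baseline covariate, completed before allocation is known. This matters because the scale is self-rated and the Day 0 list places glove training and issue ahead of baseline testing. State how patients without a baseline SIS are handled, since the gap will follow enrolment date.

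**NIHSS.** Either score it at weeks 12 and 24, where the mRS is already taken, or delete its change from the endpoint list and keep it as a baseline descriptor. If follow-up is complete, only deletion is open.

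**Cost.** At minimum, wording changes to Aim 3 and the endpoint list. If assessments are added: one questionnaire at one existing visit, one brief scale at two existing visits, matching edits to Table 1, the visit lists and the case report forms, and ethics review of the amendment at each site. No extra visits or staff.

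### Two graded secondary endpoints (mRS and manual muscle testing) are set as change scores without their own baseline grade as a covariate, which can give up power that the collected data would supply at no cost

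*Combined protocol and SAP*

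**What the plan says.** The Data analyses section of the combined protocol and SAP states: "Secondary efficacy endpoints are changes in scores on the upper extremity Fugl-Meyer Scale, modified Rankin Score, total NIHSS score, Manual Muscle testing". For muscle testing it lists five muscle groups and gives no rule for combining them. It then gives a single model for every endpoint: "Differences between treatment groups will be assessed using a generalized linear model (GLM) that accounts for repeated measures". The assessments it lists for that model include baseline itself. It adds an adjustment for baseline imbalance, without naming which variables or saying that each scale's own baseline value will be included. No distribution, link or ordinal method is named. The threshold is common to all endpoints: "We will use a two-sided test with an alpha of 0.05 to declare significance".

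Table 1 schedules the mRS and muscle testing at baseline, week 12 and week 24. Neither is measured at week 6, unlike the hand test and the Fugl-Meyer. The only power statement concerns the hand test.

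**The concern.** A change score subtracts the whole baseline value. Unless baseline and follow-up are very strongly correlated, that carries baseline noise into the outcome which a regression on baseline would leave out. Because these two scales have no week-6 value, a linear repeated-measures model has little else to draw on at week 12. With complete data and baseline means estimated separately by arm, its week-12 contrast equals the difference in mean change.

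At stake is the chance of seeing a real effect on the mRS, which is the only global scale scheduled both before and after treatment: Table 1 has the NIHSS at baseline only and the Stroke Impact Scale at weeks 12 and 24 only. Leaving the model form open also allows the choice between change and covariate adjustment to be made after the data are seen.

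**Working it through.** **The plan's own figure.** The sample-size text says "we assume to see an 11.0-point improvement on the JTHF" with the glove, "a 3.0-point improvement in control subjects", and "a standard deviation of the change score of 2.0". The difference is 11.0 − 3.0 = 8.0. With 80 patients allocated 1:1, the standard error is 2.0 × √(2/40) = 0.447, and 8.0/0.447 = 17.9 standard errors, so power is about 100%. With 20 per arm it is 8.0/0.632 = 12.6, again about 100%. The statement that "we will have more than 90% power to show a significant effect of the use of the Smart Glove on our primary efficacy outcome" therefore reproduces on its own inputs, but it says nothing about the mRS or muscle testing.

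**Why subtraction costs power.** Take equal variance σ² at both visits and correlation ρ. The change score has variance 2σ²(1 − ρ). The outcome conditional on baseline has variance σ²(1 − ρ²). Their ratio is (1 + ρ)/2: 0.65 at ρ = 0.3, 0.75 at 0.5, 0.85 at 0.7 and 0.95 at 0.9. The loss shrinks as ρ approaches 1.

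For an ungraded outcome, an assumed shift of 0.6 SD and 40 per arm, power is Φ(0.6/SE − 1.96):

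| ρ | SE, change = √(4(1 − ρ)/40) | Power | SE, on baseline = √(2(1 − ρ²)/40) | Power |
|---|---|---|---|---|
| 0.3 | 0.265 | 62% | 0.213 | 80% |
| 0.5 | 0.224 | 76% | 0.194 | 87% |
| 0.7 | 0.173 | 93% | 0.160 | 96% |
| 0.9 | 0.100 | about 100% | 0.097 | about 100% |

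**With mRS grades.** The following are assumptions, none from the documents: baseline grades 0–4 of 2/13/25/30/30%, control week-12 grades of 10/25/30/22/13%, a 0.6 SD latent shift, 40 per arm and no dropout. The methods are a t-test on change, linear regression on baseline grade, and proportional odds with baseline grade. Power from 600 runs per setting (Monte Carlo SE about 2 points):

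| Latent ρ | Change | Linear on baseline | Proportional odds | Proportional odds − change |
|---|---|---|---|---|
| 0.3 | 57% | 73% | 73% | 16 |
| 0.5 | 71% | 81% | 81% | 10 |
| 0.7 | 84% | 90% | 91% | 7 |

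Repeat simulations of 300 to 400 runs put the gap at 17–19, 12–13 and 5–7 points at these three correlations, and at 0 to 2 points at ρ = 0.9. Across all runs at ρ = 0.3 to 0.7 the gap is therefore 5 to 19 points.

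**Other assumptions.** A further grid used two other mRS distributions and common odds ratios of 2 to 3. Examples at 40 per arm:

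- Odds ratio 3, ρ = 0: change 51%, linear on baseline 75%, proportional odds 78% (gap about 27).
- Odds ratio 2, ρ = 0.2: 31%, 42%, 44% (gap about 13).
- Odds ratio 3, ρ = 0.6: 86%, 90%, 91% (gap about 5).
- Odds ratio 3, ρ = 0.9: 99.3% for all three (gap 0).

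With smaller latent shifts the gap was 3 to 6 points at 0.3 SD (ρ = 0.5 to 0.9, power 26–58% whichever method is used) and 1 to 5 points at 0.2 SD (power at most 27%).

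**Where the loss comes from.** Linear regression on baseline also treats all steps as equal, yet it recovers nearly all of the gap: in the first example 24.1 of 26.7 points. Proportional odds added about −1 to 3 points over it at 40 per arm.

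**Null behaviour.** The change-score test rejected at close to 5%. In the further grid the proportional-odds likelihood-ratio test rejected 5.0–7.5% at 40 per arm and about 6–7% at 20 per arm, so part of its small extra gain is mild excess rejection.

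**The case against.** The strongest reply is that the plan does not name a t-test on change. It names a generalized linear model with link and distribution unstated, with some baseline adjustment. A repeated-measures model that constrains the arms to equal baseline means has essentially the efficiency of regression on baseline, and the sponsor may intend that. This stands in part: the loss applies to one natural reading, not to every reading. But the endpoint is defined as change, baseline is listed among the repeated assessments, and the adjustment depends on imbalance and names no scale's baseline. Nothing in the text secures the efficient form.

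High correlation, where the loss disappears, is also possible. The trial admits both subacute and chronic patients with no limit on time since stroke, and its background describes chronic patients as having plateaued. That stands, and it is why a range is given.

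Stronger readings are tempting, but the documents do not support them:

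- That treating grade steps as equal is what costs power. A linear model with the same assumption recovers nearly everything.
- That the trial loses a fixed amount, such as the 7 to 16 points in the 600-run table. This depends on assumed inputs.
- That the repeated-measures structure is useless for these scales. Week 24 can still inform the estimate when week 12 is missing.
- That muscle testing loses the same power, or that deaths distort the result. Neither was computed, the simulations contain no deaths, and patients unlikely to reach week 24 because of limited life expectancy are excluded.

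**Conclusion.** The point holds as a matter of efficiency and specification for secondary endpoints. As written, and read as a linear model with free baseline means, the week-12 mRS and muscle-testing comparisons reduce to differences in mean change. That analysis is valid but gives up precision that the collected baseline grade would supply.

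For the mRS the power given up is about 0 points at a correlation near 0.9, about 5 to 19 points at 0.3 to 0.7 with a 0.6 SD shift, and up to about 27 points at zero correlation. All of these rest on assumed distributions, effects and correlations, with 40 per arm and no dropout. Nearly all of the loss comes from subtracting baseline. The ordinal form's separate merits are interpretive: it drops the equal-step assumption and gives any death a defined place. No size is claimed for muscle testing. A reader might infer that the trial's main conclusion is at risk; it is not, because the primary hand-test result and its power statement do not depend on these endpoints.

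**What to change.** In the Data analyses section:

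- **mRS:** replace change in score with the week-12 grade over its full ordered range. Include baseline mRS as a prespecified covariate whatever imbalance is observed. Preferably use proportional-odds regression, place any death in the worst grade, and report a common odds ratio with 95% CI.
- **Manual muscle testing:** analyse the week-12 sum over the five listed muscle groups, with the baseline sum as a covariate.
- **Model:** state the distribution and link for each of these endpoints.

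This is a wording change with no new data or visits. The small downside is that the mRS effect becomes an odds ratio under a proportional-odds assumption instead of a mean difference in grades, and the likelihood-ratio test may reject slightly above 5% at this sample size. Linear regression of the week-12 grade on arm and baseline grade would keep a mean difference and nearly all of the gain, and could be reported alongside.

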Regaining upper extremity function is very important for stroke survivors to increase their independence and ability to perform ADLs. The large majority of outpatient stroke rehabilitation currently takes place in a therapy clinic; however, access is often limited by resource allocation, financial hardship, and transportation difficulties. The Smart Glove is unique in its portability, ease of use, and low cost. It could easily be provided to stroke patients with limited financial resources and, because of its portability, can be shipped to patients in more geographically remote areas who have limited access to regular therapy services. Thus, if successful, this research could lead to a novel rehabilitation method that provides value-based care to a large proportion of stroke patients with impaired arm function.

Study Sites

Stanford University will be the Coordinating Center for this study. Patients will be recruited from the Inpatient Stroke Unit, the Outpatient Stroke Clinic, or Stanford-affiliated Acute Rehabilitation Units. Stanford's CTRU and the Neurology Outpatient Clinic will be used for study visits and assessments. Other non-Stanford affiliated sites will be invited to participate and will require separate IRB approval per their institution. A total of 80 patients will be included.

Patient Population

Patients will be eligible for the study if they (1) have a history of an ischemic or hemorrhagic stroke and (2) have impaired arm/hand function secondary to the stroke (see below for specific inclusion and exclusion criteria). We will recruit 40 patients over a 4-year period at Stanford's acute care hospitals, acute rehabilitation units, and outpatient facilities. The doctor and/or research coordinator may introduce the study to potential candidates in-person in the aforementioned sites, and the research coordinator may contact potential candidates by phone after the doctor's referral. Enrolled patients will be randomized (1:1 ratio) to standard

rehabilitation therapy versus standard rehabilitation therapy plus Smart Glove use. All patients will be allowed to participate in any scheduled outpatient rehabilitation during the study. Patients who are randomized to the Smart Glove treatment arm will take the Smart Glove with them if they transition between facilities; for example, if they transition from the acute hospital to an acute rehabilitation facility or to home.

Inclusion Criteria:

- (1) a diagnosis of ischemic or hemorrhagic stroke

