- (2) unilateral hand/arm weakness from stroke with indication for upper limb rehabilitation therapy.
- (3) ability to successfully play 2 out 4 pre-selected test games with the Smart Glove. The test specific games and criteria for passing are as follows:
 - Pour the wine (Pronation/Supination): **make 5 pours in first 1 minute**
 - Snow Ball Fight (Wrist Flexion/Extension w/ gravity eliminated): **take down 3 objects in first 1 minute**
 - Scrub the Floor (Wrist Radial/Ulnar deviation w/ gravity eliminated): **scrub the floor 5 times in first 1 minute**
 - Float the Fish (Finger Flexion/Extension): **make 50 meters with 3 or less bumps in first 3 minutes**

Exclusion Criteria:

- (1) Age <18 years
- (2) history of visually provoked seizures.
- (3) psychological disorder that could impede participation.
- (4) pre-existing neurologic disorder which causes significant deficits in arm/hand function (e.g. Parkinson's disease, peripheral neuropathy, etc.).
- (5) severe receptive aphasia which results in inability to participate with the Smart Glove.
- (6) cognitive impairment which results in inability to participate with the Smart Glove.
- (7) severe pain impeding upper extremity rehabilitation and use of the Smart Glove.
- (8) limited life-expectancy which makes it unlikely that patient will be able to complete the 24-week follow-up visit
- (9) any medical or other condition that, in the opinion of the investigator, makes the patient unsuitable for participation in this study.

Randomization: Once the participant has given informed consent and enrolled in the study, they will be randomized in a 1:1 ratio to Smart Glove therapy plus usual care versus usual care alone. A dynamic stratification system will ensure well-balanced subgroups. The randomization algorithm will employ biased-coin minimization and the variance method with stratification weights (8). The strategy is to balance treatment assignment along the marginal distribution of each stratification factor. The stratification factors used, will be: 1) age, 2) time from symptom onset to enrollment, 3) finger extension muscle testing score at enrollment, and 4) study site.

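### The primary model adjusts only for undefined baseline imbalances, so it will usually omit most of the four minimization factors; naming them as fixed covariates is a cheap gain in precision if they predict JTHFT change

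*Combined protocol and SAP*

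**What the plan says.** Under Randomization: "The randomization algorithm will employ biased-coin minimization and the variance method with stratification weights". The stated purpose is marginal balance: "The strategy is to balance treatment assignment along the marginal distribution of each stratification factor". The factors are "1) age, 2) time from symptom onset to enrollment, 3) finger extension muscle testing score at enrollment, and 4) study site". The coin probability, the weights and the factor levels are not given.

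Under Data analyses: "The primary efficacy outcome is the change in score on the Jebsen Taylor Hand Test between baseline and week 12". The model is a GLM that "accounts for repeated measures (assessments at baseline, 6 and 12 weeks for primary outcome"), followed by the one covariate rule in the document: "and will be adjusted for imbalances in baseline variables". That section does not define an imbalance, name a covariate or say how one enters the model. The power statement uses improvements of 11.0 and 3.0 points and "a standard deviation of the change score of 2.0". Study Sites gives the size: "A total of 80 patients will be included".

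**The concern.** The allocation and the analysis pull in opposite directions. Minimization removes much of the four factors' contribution to the error of the treatment estimate. The standard error reflects that only if the factors are in the model. A rule triggered by observed imbalance selects against exactly these factors, because the design has made them look balanced. Their variance then stays in the residual. To the extent that they predict JTHFT change, the interval is too wide and the test rejects less often than 5% under the null.

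Two further matters follow from the same clause. First, which covariates enter depends on the observed data and an unstated threshold, so the set could be settled after results are known. Second, baseline is listed among the repeated outcomes. In such a model a covariate entered as a main effect shifts all visits equally and largely cancels from the change from baseline to week 12. The clause could therefore be followed to the letter with little or no effect on the primary contrast.

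**Working it through.** **Inputs from the document.** Total 80, 1:1, so 40 per arm; difference 11.0 − 3.0 = 8.0; SD of change 2.0; two-sided alpha 0.05.

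**Assumptions, not in the document.** R² is the share of JTHFT-change variance that the four factors explain: 0, 0.1, 0.2, 0.35 or 0.5. Variance-method minimization, coin 0.8, equal weights, factors with 2, 3, 3 and 2 levels. Least squares on the week-12 change score stands in for the repeated-measures model. 10,000 replicates unless stated.

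**1. The plan's power.** SE = 2.0 × √(2/40) = 0.447, and 8.0/0.447 = 17.9 standard errors. Power is near 100%, so the claim of more than 90% is reproduced. It remains near 100% with or without the factors.

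**2. Half-width by formula.**
- Without the factors: t(78) × 0.447 = 1.991 × 0.447 = 0.89.
- With them (1 + 2 + 2 + 1 = 6 degrees of freedom spent): t(72) × 0.447 × √(1 − R²) = 1.993 × 0.447 × √(1 − R²). At R² = 0.2 this is 0.891 × 0.894 = 0.80; at R² = 0.5 it is 0.891 × 0.707 = 0.63.

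**3. Simulation at N = 80.** The matching column fits the coding through which the factors act. The mismatched column (1,500 replicates) is an adverse case: linear terms are fitted while onset time and finger extension act through their middle category.

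| R² | Half-width, no factors | All four, matching | All four, mismatched | Type I error, no factors (categorical / continuous effects) |
|---|---|---|---|---|
| 0 | 0.89 | 0.89 | 0.895 | 5.1% / 5.1% |
| 0.1 | 0.89 | 0.85 | 0.877 | 4.1% / 4.4% |
| 0.2 | 0.89 | 0.80 | 0.858 | 3.2% / 3.6% |
| 0.35 | 0.89 | 0.72 | 0.831 | 1.8% / 2.6% |
| 0.5 | 0.89 | 0.63 | 0.799 | 1.0% / 1.6% |

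With all four factors and matching coding, type I error is 5.1–5.2%. In the mismatched case it stays conservative: 3.9% at R² 0.2 and 2.2% at 0.5.

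**4. What an imbalance rule selects at N = 80.** The mean number of the four factors flagged is 0.8 to 1.5 at a standardized difference above 0.1, and 0.02 to 0.2 above 0.25. All four enter at the 0.1 threshold in 0.3–1.6% of trials. A separate simulation with four binary factors and a p < 0.10 trigger selected essentially none. Under the 0.1 rule the half-width is 0.86–0.87 at R² 0.2 and 0.80–0.85 at R² 0.5, so the rule recovers only part of the available gain.

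**5. Power at a smaller effect.** At an assumed 0.5 SD (0.5 × 2.0 = 1 point, against the planned 8.0), for R² 0/0.1/0.2/0.35/0.5: 60/60/61/61/62% without the factors and 59/64/69/78/88% with them.

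**6. Covariates chosen after results (3,000 replicates).** Assume five further baseline variables are also available (JTHFT, Fugl-Meyer, MMT, mRS, NIHSS; pairwise correlation 0.5). Reporting the best of six rules, namely no adjustment or a threshold between 0.1 and 0.3, gives type I error of 5.0–7.0% at N = 80, depending on how prognostic the variables are.

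**7. Main effect against visit interaction.** One simulated data set with baseline, week 6 and week 12 as outcomes, complete data, unstructured covariance and R² 0.35 gave these week-12 change contrasts:
- no covariates: 0.4603 (SE 0.1940)
- factor main effects: 0.4603 (SE 0.1940)
- factor-by-visit terms: 0.4072 (SE 0.1545)

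In another complete data set nothing changed under unstructured or compound-symmetry covariance. Under AR(1) the estimate was unchanged and the SE moved from 0.523 to 0.512.

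**The case against.** The strongest reply is that nothing in the plan's own figures changes. Power is near 100% either way, and every precision gain needs an R² that the document does not supply. At R² = 0 the fix slightly widens the interval. All of this stands. It limits the point to an inexpensive improvement but does not remove it: the sponsor chose these factors to balance on, and the precision of the estimate matters as well as the test.

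It is also fair that the gains depend on coding. The mismatched column shows that much of the gain can be lost, so the matching column gives upper bounds.

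Four stronger readings are tempting, and the document does not support them:
- A reader might infer that the rule favours the glove. Applied mechanically, it is nominal at R² = 0 and conservative above that.
- A reader might use 40 patients, where 2.0 to 2.3 of the four factors are flagged at 0.1. Patient Population gives 40 as recruitment at the coordinating center's own facilities; Study Sites gives 80 as the total.
- A reader might cite the error from searching all 512 possible covariate sets (10–19% at N = 80). The plan proposes no such search. The supportable statement is that an undefined rule permits a choice after the fact, with modest possible inflation.
- A reader might say that a main-effect covariate can never alter the primary result. That holds for complete data under unstructured or compound-symmetry covariance. The plan names no structure, and under others the SE may shift slightly.

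**Conclusion.** The point holds as a cheap improvement. The clause is a stated data-driven rule that tends to discard the variables used in the allocation, and nothing else in the document fixes the covariate set. At N = 80 and SD 2.0, naming the factors could shorten the half-width from 0.89 to at best 0.85, 0.80, 0.72 or 0.63 at R² 0.1, 0.2, 0.35 or 0.5. That is a reduction of up to 1 − 0.80/0.89 = 10% at R² 0.2 and 1 − 0.63/0.89 = 29% at R² 0.5. If the factors predict nothing, there is no gain. The sizes rest on the assumed R², coin and factor levels, and on a coding close to how the factors act. The conclusion that the covariate set is open, and depends on the observed data, rests on none of these.

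**What to change.** Replace the imbalance clause with wording such as:

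*The primary comparison of change from baseline to week 12 is adjusted for age, time from onset, finger-extension score and site, whatever their observed balance. Each is entered with its visit interaction and coded as in the minimization (or another coding fixed before unblinding), with small sites pooled. Baseline JTHFT is either a repeated outcome as now stated or a covariate by visit, not both.*

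State the minimization categories and the pooling limit; fewer than 8 patients would be one reasonable choice. Move adjustment for chance imbalance in other baseline variables to a sensitivity analysis with a stated threshold, for example a standardized difference above 0.25.

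The cost is a few sentences and a few degrees of freedom; the covariates are already collected. If the four factors explain nothing, the simulated half-width at N = 80 goes from 0.887 to 0.893–0.895, and 0.895/0.887 = 1.009, about 1%. That figure covers the four factors only; entering baseline JTHFT as a covariate would use a little more.
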